12.0 Data Management

- All data will be kept on a password protected MUSC server and in a REDCap database. All paper data sheets will be kept in a locked cabinet, in a locked office that only IRB approved study team members have access to. Participants will be given a study ID number that will be used to identify them throughout the study.
- The primary outcome of interest is duration of analgesia as demonstrated by morphine equivalents per kg of body weight given in the first 24 hours after surgery.
- Secondary outcomes observed include charted pain scores and reported side effects such as nausea/vomiting or pruritis in the first 48 hours as well as patient/family satisfaction, sedation, length of hospital stay, length of PACU stay, and analgesia for hospital stay, the numerical value for SPO2, SPO2 trend, and use or lack thereof of supplemental O2 in PACU in 15-minute intervals for up to two hours after arrival there.

Demographic and clinical characteristics will be described and compared across the two groups using appropriate statistical tests (Chi-squared tests of homogeneity for categorical variables and t-tests for equality of means, etc.). Significant covariates will be assessed for inclusion in modeling. General linear regression methods will be

used to assess the association of post-surgery MMEs with group (QL vs ITM) adjusted for associated covariates.

Our primary hypothesis is that subjects in the two groups will consume different amounts of post-surgery MMEs. Based on preliminary data from a similar study, we assume that MME/kg consumption in the QL block group will be 0.07 ± 0.076 .

Summary Statements

Assuming a normal underlying distribution, group sample sizes of 12 and 12 achieve 80% power to detect a difference of 0.1 MME/kg between the null hypothesis that both group means are 0.07 and the alternative hypothesis that the mean of group 2 is 0.17 with known group standard deviation of 0.076 and with a significance level (alpha) of 0.05000 using a two-sided Mann-Whitney test. As we anticipate a non-normal distribution, we will inflate sample size by 15%. We will inflate the sample size further by 10% to account for withdrawals.

The final inflated sample size will be 15 per group.

Two-tail test that QL < ITM

$H_0 = \text{Mean}_{QL} = \text{Mean}_{ITM}$

$H_a = \text{Mean}_{QL} \neq \text{Mean}_{ITM}$

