Intrathecal Morphine versus Bilateral Quadratus Lumborum Blocks for Perioperative Analgesia in Pediatric Patients Undergoing Open Lower Abdominal Procedures: A Prospective Randomized Trial

NCT05506930

July 13, 2023

PROTOCOL TITLE:

Intrathecal Morphine versus Bilateral Quadratus Lumborum Blocks for Perioperative Analgesia in Pediatric Patients Undergoing Open Lower Abdominal Procedures: A Prospective Randomized Trial

PRINCIPAL INVESTIGATOR:

[name].

- **Objectives / Specific Aims**

- We hypothesize that intrathecal morphine will have superior analgesia as demonstrated by charted pain scores and morphine equivalents in the first 24 hours.
- We hypothesize that intrathecal morphine will have higher incidence of side effects when compared to quadratus lumborum blocks

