4.0 Study Endpoints

- The primary endpoint will compare the effect that intrathecal morphine and quadratus lumborum blocks have on the duration of analgesia as demonstrated by charted pain scores and morphine equivalents in the first 24 hours.
- The secondary endpoint will assess the side effects of each intervention such as nausea and vomiting, and pruritis. Other secondary endpoints will include patient/family satisfaction, sedation, length of hospital stay, length of PACU stay, and analgesia for hospital stay (as approximated at 48 hours).

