10.0 Study Design / Methods

- This prospective, randomized, blinded study will attempt to determine if intrathecal morphine provides superior analgesia postoperatively for open lower abdominal procedures when compared to bilateral quadratus lumborum blocks. It will also assess side effects of both pain interventions.
- Once a parent/guardian provide written informed consent, subjects will be assigned a number with a corresponding group. Randomization will be performed by a statistician prior to enrollment and assigned based on the patient's enrollment number. Subjects will be assigned to one of the following groups: 1) Intrathecal Morphine: spinal (neuraxial) dose of preservative free morphine (duramorph), usually about 4-5mcg/kg, or 2) Quadratus Lumborum Block: peripheral nerve block utilizing ropivacaine 0.2%, usually about $\frac{1}{2}$ mL per kg per side (total dose approximately 1mL/kg). The total dose of administered medication (duramorph or ropivacaine) is at the discretion of the anesthesiologist but will be within the dose range as stated above.
- The operating room pharmacist will follow the randomization to prepare or provide the correct medication. Intrathecal morphine will be prepared by the operating room pharmacist. Local anesthetic vials for quadratus lumborum blocks will be obtained from the pharmacy and the medication will be drawn into a syringe by an anesthesiologist who is part of the research team prior to injection. The dosage prepared and administered will be based on weight.
- The pharmacist will not be blinded to the randomization. Nor will the operative team. The study team member who completes data collection from the family and chart review will be blinded to randomization. In addition, the parent and child will also be blinded to the type of block that is used.
- The intervention will be administered in the operating room after the subject is under general anesthesia but prior to incision, as per usual practice. The block will be performed by a study team member board certified in pediatric anesthesiology. Quadratus lumborum blocks are placed using ultrasound guidance, local anesthetic is injected in the fascial plane using aseptic technique. Intrathecal morphine is accomplished by injection of preservative-free morphine in the intrathecal space in the lumbar region using sterile technique.

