- Approximately 24 hours after the procedure, a research team member will ask the parent/guardian about side effects such as nausea, vomiting, itching, etc. The research team member will also ask the family if they were satisfied with the subject's pain control postoperatively and overall experience. If a family member or guardian is not present, a care team member will be asked about side effects and the patient's chart will be reviewed for notes pertaining to side effects.
- The patient's chart will be used to see if and how much narcotic pain medication was administered in the first 48 hours after the procedure as well as documented pain scores up to 48 hours after the procedure ends. The chart medication administration record will also be used to identify administration of rescue medications for nausea

or itching non-opioid medications such as acetaminophen or ibuprofen, or other medications such as diazepam or oxybutynin.

Table 1. Baseline and Intraoperative Assessments	
Demographics	
Baseline	
Pre-op meds including opioids in past 24 hours	
Randomization	
Anesthesia intra-op data	
Surgical techniques	
Adverse Events	

Table 2. Post-Op Follow Up Assessments		
Outcome Measure	Instrument	Collected
Pain Scores	Charted pain scores	24 and 48 hrs. post-op
Pain Control Satisfaction	Parent/Guardian Satisfaction	24-hours post-op
Side Effects Experienced	Parent/Guardian Satisfaction	24-hours post-op
Overall Satisfaction	Parent/Guardian Satisfaction	24-hours post-op
Opioid Consumption	MME Consumption	24 and 48 hrs. post-op
Side Effects and Adverse Events	Adverse Events	Assessed through post-op hours 0-48
Medications	Medications used to control or relieve side effects	24 and 48 hrs. post-op

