15.0 Risks to Subjects

- If a parent chooses for their child not to participate, the risk is the same since regional anesthesia is part of standard care at MUSC and will be offered regardless of study participation. Both study medications have been routinely used in practice at MUSC for over ten years.
- Subjects will be assigned to receive intrathecal morphine or a quadratus lumborum block by chance. One group may prove to be less beneficial than the other.
- Intrathecal Duramorph/Morphine: the use is well established in pediatric patients even though it is not FDA approved for use in children, but is commonly used in this population and at this institution for this indication. Other risks include infection at site of injection (less than 1%), damage to surrounding structures (less than 1%), block failure (1%) headache and cerebral spinal fluid leak (7%), Urinary retention (6%), Nausea and vomiting are the most common risks/side effects occurring in less than 10% of patients. Itching occurs in 20-40% of patients. Literature states that patients recover from side effects and are not long term.

QL Block/Ropivacaine: complications/risks are rare but include local anesthetic systemic toxicity (less than 0.01%), block failure (1%), bleeding and infection at block site (less than 1%), damage to surrounding structures (less than 1%), allergic reaction (rare, less than 1%), neurological complications (less than 1%). Literature states that patients recover from side effects and are not long term.

- There is a risk of loss of confidentiality.

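### Side effects are defined as 48-hour reported events but collected mainly from one parent interview at about 24 hours, with chart notes used unevenly and rescue drugs never linked to the symptom.

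*Combined protocol and SAP*

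**What the plan says.** The second hypothesis, in Objectives / Specific Aims, is directional: "We hypothesize that intrathecal morphine will have higher incidence of side effects when compared to quadratus lumborum blocks". Section 4.0 turns it into an endpoint: "The secondary endpoint will assess the side effects of each intervention such as nausea and vomiting, and pruritis". Section 12.0 adds a source and a window: "reported side effects such as nausea/vomiting or pruritis in the first 48 hours".

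Collection is described in Section 10.0. The main source is an interview: "Approximately 24 hours after the procedure, a research team member will ask the parent/guardian about side effects such as nausea, vomiting, itching, etc". If no family member or guardian is there, "a care team member will be asked about side effects and the patient's chart will be reviewed for notes pertaining to side effects". Drugs come from another source: "The chart medication administration record will also be used to identify administration of rescue medications for nausea", and the sentence goes on to itching and to other medications.

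Table 2 has a side-effect row at 24 hours answered by the parent or guardian, a row for side effects and adverse events over hours 0-48, and a separate row, under the outcome-measure heading, for drugs used against side effects at 24 and 48 hours.

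On blinding, Section 10.0 says: "The pharmacist will not be blinded to the randomization. Nor will the operative team". The data collector, parent and child are blinded. On expected frequency with intrathecal morphine, Section 15.0 says: "Itching occurs in 20-40% of patients".

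**The concern.** Three features of the plan do not fit together.

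- **Window.** The outcome runs to 48 hours. The only interview is at about 24 hours.
- **Source.** A child whose parent is present is described as assessed by interview. A child whose parent is absent is assessed from a care team member and the chart notes. The two routes need not find the same events.
- **Link.** A drug given for itching or nausea is evidence that the effect occurred or was suspected. It is recorded, but nothing says whether it makes the child a case.

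A child treated for itching whose parent did not notice or recall it, or whose itching began after the interview, could therefore be recorded as having no reported side effect. Section 12.0 specifies a model only for morphine milligram equivalents (MMEs), so how symptoms and drugs are to be weighed for the second hypothesis would be settled after the data are seen.

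There is also a possible bias between arms. If children given intrathecal morphine were treated earlier or more often for these effects, the difference in reported symptoms would shrink although the burden had only moved into drug use. Blinding the parent and the data collector would not prevent this, because it acts before the interview.

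**Working it through.** **1. The sources side by side**

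| Source | Which children | Period covered | Linked to the symptom outcome? |
|---|---|---|---|
| Parent interview | Family present | Up to about 24 h | Yes |
| Care team member and chart notes | Described only when family absent | Not stated | Yes |
| Table 2 side-effect and adverse-event row | All | 0-48 h | Not stated; no instrument or definition for nausea or itching |
| Medication record, rescue drugs | All | 24 and 48 h | No rule given |

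For a child with family present, the only named source of symptoms stops at about 24 hours, half of the outcome window. The 0-48 hour row implies more collection but does not say from what.

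**2. The plan's own figure**

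Section 12.0 gives a sample size only for MME/kg: 12 per group, inflated by 15% and then 10%. 12 × 1.15 × 1.10 = 15.18, against a stated 15 per group. There is no sample size or power for side effects, so no stated figure is in error here. The 15 per group is used below.

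**3. Expected events**

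At the protocol's 20-40% itching, the morphine arm expects 15 × 0.20 = 3 to 15 × 0.40 = 6 children. If one third were missed, 2 to 4 would remain.

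**4. Illustration of what missed events could cost**

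Inputs from the documents: 15 per arm; true itching rate p of 20% or 40% with intrathecal morphine. Assumptions, given nowhere in the documents: QL itching rate q of 0%, 5% or 10%; a missed share m of one third, in the morphine arm only; Fisher's exact test, two-sided, alpha 0.05.

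Observed morphine-arm rate = p × (1 − m):

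- 0.40 × 2/3 = 26.7%
- 0.20 × 2/3 = 13.3%

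Power = Σ over x, y of Bin(x; 15, observed rate) × Bin(y; 15, q) × [Fisher p(x, y) ≤ 0.05].

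| Assumed QL rate | True 40%: none missed → one third missed | True 20%: none missed → one third missed |
|---|---|---|
| 0% | 78% → 37% | 16% → 4% |
| 5% | 52% → 20% | 8% → 2% |
| 10% | 33% → 10% | 4% → 1% |

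The test is coarse at this size. With no QL event, 5 morphine-arm events are needed for p ≤ 0.05; with one QL event, 7. Losing one or two events can decide the result.

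**5. What the illustration does not show**

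It puts every missed event in one arm. Misses spread over both arms would also lower the counts, without the same directional bias. It also does not separate events that were treated or charted from events that were prevented; only the former can be recovered by better counting.

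**The case against.** A reader might infer that the plan judges side effects on reported symptoms alone. It does not say that. Table 2 names drugs for side effects as an outcome measure and has a 0-48 hour side-effect and adverse-event row, and the blinded collector also does chart review. The lists in Sections 4.0 and 12.0 are worded as examples. An excess of rescue drugs in one arm would be recorded and could be read beside the symptoms. This stands: the data are largely collected, and the gap is the missing rule for using them and the unclear source.

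A reader might also infer that an unblinded operative team chooses preventive drugs and so masks an excess with intrathecal morphine. The documents never mention antiemetic or antipruritic prophylaxis, do not say who orders such drugs, and do not say whether recovery or ward staff know the arm. Intraoperative drugs may fall under the anesthesia data in Table 1. Rescue normally follows a symptom, so a rescued child can still be reported at interview. Masking by arm is therefore possible but not shown.

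Finally, the power losses rest on assumed rates, and the comparison is weak anyway. Section 18.0 cites a series of 100 children with 14 cases of pruritus; at 14% against an assumed 5%, Fisher power at 15 per arm is about 2% before anything is missed. This also stands. It limits how much the correction can gain, but it does not justify counting events differently between children.

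**Conclusion.** The point holds as a gap in ascertainment and definition. The outcome covers 48 hours, the interview covers about 24, chart notes on side effects are described for only some children, and rescue drugs are collected without a rule that ties them to the symptom. This follows from the text and needs no assumption.

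That unequal drug use by arm could narrow the observed difference is an inference, made plausible by the unblinded operative team and the absence of any stated rule on these drugs. Its size is unknown. With an assumed QL rate of 5% and one third of morphine-arm events missed, power falls from 52% to 20% at a true 40% and from 8% to 2% at a true 20%. These figures show sensitivity at 15 per arm; they are not an estimate of bias.

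The outcome is secondary, and the primary MME analysis is not touched by this point. The change is worth making because it is cheap and serves one of the trial's two stated hypotheses.

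**What to change.** In Section 12.0, with a matching change in Section 10.0 and Table 2:

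1. For every child, count nausea/vomiting and, separately, pruritus as present over 0-48 hours if it was reported at interview, noted in the chart, or treated with an as-needed drug given for it. Search chart notes for all children, whether or not family is present.
2. By arm, show the report-only rate and the drug-use rate beside the combined rate.
3. From the anesthesia and medication records, tabulate by arm any antiemetic or antipruritic drugs given before symptoms. State that similar symptom rates will be interpreted in the light of that table.

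The cost is some analysis wording and a few fields from records already opened for each child. It changes no care. The downside is that a drug given without a true symptom would count as an event, which is why the report-only rate should stay visible. The combined outcome recovers only treated or charted events. Prevented ones remain uncounted, and the table in step 3 is the only guard against misreading them.

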Most abdominal surgeries will have a combination of analgesic modalities with non-steroidal anti-inflammatories and regional anesthesia used to minimize narcotic administration and its associated sedation and side effects. The most common regional techniques used at MUSC for abdominal procedures are intrathecal morphine administration, abdominal wall blocks (including quadratus lumborum blocks), and epidurals. Epidurals also potentially lead to leg weakness (and subsequent patient dissatisfaction) and require increased monitoring at this institution.

Intrathecal morphine has been shown to reduce total opioid consumption for a wide range of pediatric surgical procedures. However, significant rates of pruritis, emesis, and respiratory depression continued to be reported in a dose-dependent manner². Subsequently, low-dose intrathecal morphine (3-5 mcg/kg) was investigated and shown to reduce the incidence of pruritis, emesis, and respiratory depression^[1,4]. Fascial plane blocks have also been used for analgesia in abdominal and thoracic procedures in the

pediatric population to improve pain control and reduce postoperative narcotic administration. Quadratus lumborum blocks specifically provide analgesia for the abdominal wall (incisional pain) as well as some visceral pain relief (i.e., pain related to intraabdominal structures). The purpose of this study is to compare the postoperative analgesia provided by intrathecal morphine to that of bilateral quadratus lumborum blocks for open abdominal procedures.

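### Respiratory depression is named in the Background as a harm of intrathecal morphine but is neither a defined outcome nor in the Section 15.0 risk list, and the systematic oxygen data end within two hours of PACU arrival

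*Combined protocol and SAP*

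**What the plan says.** - **Aim (Objectives / Specific Aims).** The second hypothesis is that "intrathecal morphine will have higher incidence of side effects when compared to quadratus lumborum blocks".
- **Known harms (2.0 Background).** For intrathecal morphine, "significant rates of pruritis, emesis, and respiratory depression continued to be reported in a dose-dependent manner". The next sentence qualifies this: "low-dose intrathecal morphine (3-5 mcg/kg) was investigated and shown to reduce the incidence of pruritis, emesis, and respiratory depression". The trial uses a "spinal (neuraxial) dose of preservative free morphine (duramorph), usually about 4-5mcg/kg" (10.0), which lies inside that range.
- **Named side-effect outcomes.** Section 4.0 gives "side effects of each intervention such as nausea and vomiting, and pruritis", and Section 12.0 gives the same examples over 48 hours. The parent interview at about 24 hours (10.0) asks about nausea, vomiting and itching, with an open-ended close.
- **Respiratory data.** Section 12.0 lists SpO2, its trend and "use or lack thereof of supplemental O2 in PACU in 15-minute intervals for up to two hours after arrival there".
- **Other routes.** Table 2 has a row for side effects and adverse events over hours 0–48, with no event listed or defined. It also has a row for drugs given for side effects, at 24 and 48 hours. Sedation is a secondary outcome (4.0 and 12.0) but has no row in Table 2. Section 13.0 has adverse events recorded and reported.
- **Risk list (15.0).** The ITM entry covers infection, damage to structures, block failure, headache with CSF leak, urinary retention, nausea and vomiting, and itching (20–40%). It also states: "Nausea and vomiting are the most common risks/side effects occurring in less than 10% of patients".

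**The concern.** The plan names three harms of intrathecal morphine together. Two of them, vomiting and itching, become named outcomes and appear in the risk list. The third, respiratory depression, does neither. What the plan collects systematically on breathing ends early in the period over which side effects are compared.

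At stake is the second aim. If respiratory events after PACU enter the data only when someone chooses to chart them as adverse events, an outcome that was never looked for can be read as an outcome that did not occur. The operative team is not blinded (10.0), so an undefined event entry is also open to different recording habits in the two arms. Separately, the risk section disagrees with the plan's own Background and, on which effect is most common, with its own figures.

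**Working it through.** **1. Side by side.**

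| Harm of ITM in 2.0 | Named outcome (4.0, 12.0) | ITM risk list (15.0) | Systematic data |
|---|---|---|---|
| Itching | yes | yes, 20–40% | interview; rescue drugs to 48 h |
| Vomiting | yes | yes, <10% with nausea | interview; rescue drugs to 48 h |
| Respiratory depression | no | no | SpO2 and oxygen, PACU only, up to 2 h |

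**2. The sentence on the most common effect.** Section 15.0 gives nausea and vomiting below 10% and itching at 20–40%. The lowest itching figure is at least twice the highest nausea figure (20/10 = 2). The retrospective series of 100 children cited in Section 18.0 points the same way: 14 with itching, 9 with nausea or vomiting.

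**3. Length of the oxygen window.** 2/24 = 8.3% of the first 24 hours; 2/48 = 4.2% of the 48-hour adverse-event period. These are maxima, since data end sooner if the child leaves PACU sooner.

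**4. Number of children.** The plan's figure reproduces: 12 × 1.15 × 1.10 = 15.2, against the stated 15 per group. The base of 12 is also adequate: a simulated two-sided Mann-Whitney test (difference 0.1, SD 0.076, normal data) has 83.5% power at 12.

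**5. What under-capture could do.** The documents give no rate of respiratory depression and no timing, so both inputs here are assumptions. Let p be the true rate in the ITM arm and c the fraction of events that reach the dataset by any route. The chance of recording at least one case among 15 children is 1 − (1 − pc)^15.

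| p | c = 1 | c = 0.5 | c = 0.25 | c = 1/12 |
|---|---|---|---|---|
| 1% | 14.0% | 7.2% | 3.7% | 1.2% |
| 5% | 53.7% | 31.6% | 17.2% | 6.1% |
| 10% | 79.4% | 53.7% | 31.6% | 11.8% |

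The column c = 1 means that the adverse-event row catches everything. The column c = 1/12 means that only the PACU data catch anything and that events are spread evenly over 24 hours. The truth lies at an unknown point between.

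**6. What full capture could and could not show.** With zero cases in the block arm, two-sided Fisher's exact test gives p = 0.0996 for 4 of 15 ITM cases and p = 0.042 for 5 of 15. At least 5 of 15 are therefore needed. If the true ITM rate were 20%, the chance of 5 or more would be 16.4%; at 10% it would be 1.3%. With 0 of 15, the one-sided 95% upper limit is 1 − 0.05^(1/15) = 18.1%, whatever the quality of collection.

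**The case against.** The strongest reply is that the harm is not ignored. The outcome lists are introduced as examples, so respiratory events are not excluded. Adverse events are assessed to 48 hours and reported to the safety board. Sedation is an outcome. An opioid-reversal drug could reasonably be entered in the side-effect medication row. The Background says that doses in the trial's range reduced the incidence, and the series of 100 children at 5 mcg/kg cited in Section 18.0 had no serious adverse events.

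Much of this stands, and it rules out several stronger readings that a reader might infer:

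- **That nothing respiratory is collected after two hours.** The routes above exist. What is missing is a named, defined and uniformly collected outcome.
- **That more than 90% of events would be missed.** The 8.3% and 4.2% are shares of clock time. The documents do not say when events occur.
- **That the 18.1% limit measures the defect.** It comes from 15 children and would be the same with perfect collection.
- **That this is the most serious harm, or one specific to ITM.** The plan does not rank harms, and Section 2.0 also attributes respiratory depression to systemic opioids, which either arm may receive.
- **That families are not told of the risk.** The consent pages are not among the documents, so this cannot be judged.

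What the reply does not do is close the gap. A reduced incidence is not a nil incidence, and no rate is given. The adverse-event row defines no event, and sedation has no scale or time. The text of Section 10.0 ties side-effect rescue drugs to nausea and itching, and it describes chart review for side-effect notes as the fallback when no family member is present.

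**Conclusion.** The point holds in two separate parts.

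*Measurement.* After at most two hours in PACU, respiratory depression is left to entries that the plan does not define, so the side-effect comparison can under-count it. The size of the under-count cannot be derived from the documents; the table in the working rests on assumed rates and assumed capture. Better capture would improve the description of this harm but would not give a powered comparison at 15 per arm. The primary MME/kg analysis is unaffected.

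*Risk wording.* Section 15.0 omits a harm that Section 2.0 names, and its sentence on the most common effect contradicts its own itching figure. This needs no assumption.

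Both parts should be corrected. Neither undermines the trial.

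**What to change.** 1. Within the existing 0–48 hour side-effect and adverse-event collection, pre-define respiratory depression as a descriptive secondary safety outcome in both arms. The blinded data collector abstracts the same chart fields for every child: any opioid-reversal drug on the medication record, any supplemental oxygen after PACU, and any charted desaturation or respiratory event.
2. Report counts per arm with exact confidence intervals and state that the comparison is not powered. Record how often SpO2 was charted in each arm. The documents do not give post-PACU charting frequency, and if it differs between arms, a difference in desaturations could partly reflect a difference in monitoring.
3. Reconcile Section 15.0 with Section 2.0 by listing respiratory depression or explaining why it is left out. Correct the sentence on the most common effect against the 20–40% itching figure, and check any other text that repeats it.

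The cost is a few REDCap fields, a wording change and somewhat longer abstraction. The post-PACU oxygen fields are new: the chart review now described covers opioids, pain scores and other medications. No change to dosing, monitoring or care is proposed.

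### Section 12.0 states power for a Mann-Whitney test but analyses opioid use by covariate-adjusted linear regression, labels neither as the deciding test, and lets covariates enter on significance without excluding data recorded after the block

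*Combined protocol and SAP*

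**What the plan says.** All the analysis text is in Section 12.0 (Data Management) of the combined protocol and SAP.

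- The primary outcome is "morphine equivalents per kg of body weight given in the first 24 hours after surgery".
- Chi-squared and t-tests are assigned to demographic and clinical characteristics. Then: "Significant covariates will be assessed for inclusion in modeling".
- General linear regression is to be "used to assess the association of post-surgery MMEs with group (QL vs ITM) adjusted for associated covariates". This is the only sentence that assigns a method to opioid use.
- The next sentence reads "Our primary hypothesis is that subjects in the two groups will consume different amounts of post-surgery MMEs". It names no test.
- The Summary Statements give 80% power at 12 per group for a difference of 0.1 MME/kg (0.07 against 0.17, SD 0.076, normal data) "with a significance level (alpha) of 0.05000 using a two-sided Mann-Whitney test".
- They continue: "As we anticipate a non-normal distribution, we will inflate sample size by 15" per cent. A further 10% for withdrawals leads to 15 per group.
- The null and alternative hypotheses that close the section are equality and inequality of two means.

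In Section 10.0, Table 1 lists "Anesthesia intra-op data" and surgical techniques beside demographics, baseline data and preoperative medication. The same section places the block after induction and before incision.

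**The concern.** The powered test is not the stated analysis. Mann-Whitney appears only in the power statement. Regression appears only in the analysis text, and the hypotheses on means fit regression better, because Mann-Whitney compares means only if the two distributions differ by a pure shift. With 15 per arm and data the authors expect to be non-normal, the two tests can give different answers, and the plan does not say which one counts.

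The covariate rule is the second opening. It does not say whether a covariate must be significant between arms or against the outcome, gives no threshold and no list, and does not confine candidates to data recorded before randomisation. Table 1 includes intra-operative data, some of it necessarily recorded after the block. Adjusting for a variable that the treatment has changed no longer estimates the whole treatment effect. At stake is whether the main p-value and estimate are fixed in advance and free of that bias.

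**Working it through.** **Inputs (Section 12.0).** Means 0.07 and 0.17 MME/kg, SD 0.076 in each arm, two-sided alpha 0.05, 12 per group before inflation, 15 after. With 10% withdrawals, 15 × 0.9 = 13.5, taken as 13.

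**1. The plan's own figure.** Standardised difference 0.1/0.076 = 1.316. For the t-test, noncentrality = 1.316 × √(n/2); at n = 12 this is 3.22 on 22 df, power 0.869. Scaling n by 0.864, the lower bound on Mann-Whitney efficiency, gives power 0.771 at n = 11 and 0.810 at n = 12. So 12 is the smallest n reaching 80%, as stated. Simulated exact Mann-Whitney power at 12 per group is 0.838, so 80% is slightly conservative. Inflation: 12 × 1.15 × 1.10 = 15.2, against the stated 15.

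**2. Do the tests differ?** Simulated power (%) at 12 / 13 / 15 per arm. The gamma shapes are assumptions.

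| Data on MME/kg | Linear, unadjusted | Mann-Whitney | Tests disagree at 13 |
|---|---|---|---|
| Normal, SD 0.076 both arms | 87 / 90 / 94 | 84 / 87 / 92 | 4% of trials |
| Gamma, SD 0.076 both arms | 85 / 87 / 91 | 92 / 94 / 96 | 8% |
| Gamma, SD proportional to mean | 38 / 41 / 49 | 34 / 37 / 42 | 15% |

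In the last row the second arm's SD is 0.076 × 0.17/0.07 = 0.185. The ranking of the tests changes with the shape. Some departure from the normal is likely: Φ(−0.07/0.076) = 0.18, so a normal QL arm would have 18% of its values below zero.

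**3. Number of covariates** (normal data, SD 0.076). Two prespecified covariates explaining 0 to 25% of variance: 87 to 94% at 13 per arm. Four that explain nothing: 78 / 83 / 89% at 12 / 13 / 15. A short list keeps power; a long one can bring it just under 80% at 12.

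**4. Type I error at 13 per arm.** Either test alone: 4 to 5%. The better of the two: 6%. The smallest p-value over Mann-Whitney and every subset of 3 to 5 unrelated covariates: 8 to 11%. A significance rule applied mechanically to unrelated covariates: 4 to 5%.

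**5. A covariate recorded after the block.** Suppose that the block shifts the covariate by δ SD and that its within-arm correlation with the outcome is r, through shared patient factors. The adjusted group coefficient then moves by r × δ outcome SDs. With assumed δ = 1 and r = 0.3 to 0.5, that is 0.3 × 0.076 = 0.023 to 0.5 × 0.076 = 0.038 MME/kg, or 23 to 38% of the 0.1 difference. In simulation at 13 per arm, entering such a variable because it differs between arms raised rejection under no treatment effect to about 10 to 16%. It cut power from about 90% to 58 to 66% when the shift runs in the same direction as the effect; a shift the other way exaggerates the effect.

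**The case against.** The strongest reply is that the plan does choose. It states one between-group analysis of opioid use, the primary hypothesis follows directly in the same terms, the hypotheses are on means, and Mann-Whitney is only sample-size text whose power is conservative for an unadjusted linear model. This stands as a reading: regression is the likelier intention. It does not settle the matter, because no sentence says so and the sample size is justified by another test.

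Table 1 is a data-collection list and does not nominate covariates, and some intra-operative data precede the block. That stands too. A reader might infer that the plan intends to adjust for post-block data; the documents do not say that. They only fail to exclude it, while candidates are described as broadly as clinical characteristics.

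Other stronger readings also fail:

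- *The trial is underpowered for its stated analysis.* Not on the plan's inputs (step 1).
- *Type I error will reach 8 to 11%.* That needs a search over all tests and covariate subsets, which nothing in the plan proposes.
- *Mann-Whitney must be primary.* That is a preference. Its advantage under gamma data with equal SDs reverses when the SD rises with the mean.
- *The regression is on absolute MME or an open time window.* Section 12.0 defines the outcome per kg over 24 hours and powers it in MME/kg; Section 4.0 makes 48-hour analgesia secondary. The model wording is probably shorthand.

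**Conclusion.** The point holds as a contradiction between stated methods and as an omission: the powered test and the stated analysis differ, neither is labelled as deciding, and covariates may enter on significance without a bar on post-block data. It should be corrected, but it calls for no redesign.

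No change in sample size follows from it. On the plan's normal inputs at 12 per group, neither Mann-Whitney (about 84%) nor the unadjusted linear model (about 87%) falls below 80%. This rests on the SD of 0.076 in both arms. If the SD rose in proportion to the mean, both tests would have roughly 40% power at 13 per arm, so the result is not a general assurance of power, and neither test is uniformly the more powerful.

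Leaving the choice between the two tests open costs about one to two points of type I error. The larger risk is the post-block covariate; its size depends on the assumed shift and correlation, and the figures in step 5 illustrate it rather than predict it.

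**What to change.** Before any outcome is seen by group, amend Section 12.0:

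1. Name one primary test, on MME/kg in the first 24 hours, and use that wording in the model and hypothesis sentences.
2. Make the power statement and the null and alternative hypotheses match it, and list the other test as the sensitivity analysis.
3. Either choice is acceptable. Labelling the existing regression as primary needs the fewest changes: keep the hypotheses on means and restate power for that model. Mann-Whitney matches the existing power statement: reword the hypotheses from means to distributions and give the mean difference with its confidence interval from regression as supportive.
4. In any regression, replace the selection of significant covariates with a short fixed list of pre-randomisation variables, and exclude anything recorded after the block.

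The cost is a few sentences, with no added patients or data. What is given up is the freedom to choose test and covariates later. With the SD at the planned value, Mann-Whitney as primary loses about 3 points of power if the data are normal, and regression about 7 points if they are gamma-shaped; with the SD proportional to the mean, Mann-Whitney is the one that loses, by about 4 to 7 points.
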